16 STATISTICAL METHODS AND DETERMINATION OF SAMPLE SIZE

The principal features of the statistical analysis to be performed are described in this section. A more technical and detailed elaboration of the principal features will be presented in a separate Statistical Analysis Plan (SAP).

16.1 General

Pharmacokinetic data will be presented using summary statistics. Data will be presented in terms of number (N), arithmetic mean, standard deviation (SD), median, minimum and maximum value. In addition, for the parameters AUC and C_{max} the geometric mean and coefficient of variation (CV) will be presented.

Categorical data will be presented as counts and percentages. When applicable, summary data will be presented by treatment, and by assessment time. Individual subject data will be listed by subject number, treatment, and, where applicable, by assessment time.

The primary endpoint will be investigating a one sided hypothesis that ZYN 6mg has a lower AUC compared to 2 pouches of 8 mg Swedish snus, using a significance level of 2.5%. All other test will be two-sided with a significance level of 5%.

16.2 Determination of sample size

Former studies had showed that the AUC for the ZYN smooth 6mg has a AUC of 3581 and 2 pouches of 8 mg Swedish snus has a AUC of 5586 with a common standard deviation of 1920.

The hypothesis is that ZYN smooth 6 mg has a significant lower AUC compared with 2 pouches 8mg Swedish snus. With a power of 80% and a significance level of 2.5% will the number of subjects needed be 32, assuming 10% drop out rate a total of 36 subjects will be included.

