8 STUDY DESIGN

8.1 Overall study design and schedule of events

The study will be conducted as an open, randomized, seven-way cross-over, single dose administration. The study will include 36 subjects.

The subjects included will be healthy males and females aged ≥ 19 years who have used tobacco-based snus for ≥ 1 year with a weekly consumption of three or more snus cans (brands with nicotine content $\geq 1\%$). Subjects who are pregnant or who have a history of hypertension or any cardiovascular disease are excluded. Subjects shall be abstinent from snus and all other nicotine containing products from 8.00 p.m. the night before each trial day.

Before entry to the study subjects undergo screening, evaluations including smoking and snus use, medical history and collection of height and weight.

Subjects report to the clinic on separate days for the seven (7) experimental sessions in addition to visits for screening and follow-up. Between each experimental session a washout period of at least 24 hours is required. The subjects are instructed to abstain from snus or other nicotine delivery products as from 8.00 p.m. the evening before and to refrain from smoking 24 hours before each experimental session. All sessions are performed during the morning hours to facilitate abstinence. The subjects should certify abstinence before each treatment is started.

The treatments are administered as single doses in a pre-determined randomized order. The subject keeps the pouch still between the upper lip (lower lip for treatment 4) and the gum for 60 minutes and are instructed not to manipulate the pouch with the tongue or lips. The subjects are instructed not to eat, drink, chew chewing gum or brush teeth from 30 minutes before application of treatment, during application of investigational products and 30 minutes after the investigational product have been taken out (Henningfield et al 1990)³.

After 60 minutes the pouches are collected and frozen (-20°C) pending analyses of nicotine.

Blood samples for assessment of plasma levels of nicotine and Methyl salicylate will be collected at pre-defined time points from pre-dose to 6 hours after IP administration.

Table 8.1-1 Schedule of events

Visit	Visit 1 ¹ Screening	Visit 2-8 ² Cross-over	Visit 9 Telephone FU
Assessments / Study days	-28 to -1		7 days(-3/+7) after last dose
Informed consent	x		
Demographics	X		
Medical/surgical history	x		
Inclusion/exclusion criteria	x		
Physical examination	x		
Weight, height	x		

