8.2 Rationale for study design

A crossover design was chosen to yield a more efficient comparison of treatments than a parallel study design, i.e., fewer subjects are required since each subject will serve as his own control. To avoid carryover effects, a wash-out period of at least 24 hours has been incorporated between administrations.

Randomisation will be used to minimise bias in the assignment of subjects to a treatment sequence and to increase the likelihood that known and unknown subject attributes (e.g., demographic and baseline characteristics) are evenly balanced across treatment groups.

Prospective approval of protocol deviations to eligibility criteria, also known as protocol waivers or exemptions, is not permitted.

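### The 32 subjects stated for 80% power match two independent groups of 16, not this crossover with a paired primary test, so Section 16.2 understates the power

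*Protocol*

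**What the plan says.** Section 16.2 takes its inputs from former studies. For the test product it states that "the AUC for the ZYN smooth 6mg has a AUC of 3581". The comparator, a double pouch of snus, is put at 5586. The spread is given once for the two products, "with a common standard deviation of 1920". The section concludes "With a power of 80% and a significance level of 2.5% will the number of subjects needed be 32" and then, "assuming 10% drop out rate a total of 36 subjects will be included". Section 16.1 fixes the direction: "The primary endpoint will be investigating a one sided hypothesis that ZYN 6mg has a lower AUC". Section 16.2 names no test or formula, and gives neither a within-subject correlation nor an SD of the paired difference.

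The design is set out in Section 8.1: "The study will be conducted as an open, randomized, seven-way cross-over, single dose administration". Section 8.2 defends the crossover on the ground that "fewer subjects are required since each subject will serve as his own control". Section 16.5.1 plans a signed Wilcoxon test for the primary AUCinf comparison. Section 16.3.2 restricts the PK analysis set to subjects who complete the study without major deviations.

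**The concern.** Every subject who completes the study uses both products of the primary comparison. Thirty-two evaluable subjects are therefore 32 pairs of AUC values, and the precision of the comparison depends on the SD of the within-subject difference. Section 16.2 gives only an SD common to the two products, which is what a comparison of two separate groups needs. The number it reaches shows no trace of the saving that Section 8.2 claims for the crossover.

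At stake is the truth of the power statement and, with it, the stated reason for enrolling 36 volunteers. Each of them attends seven product sessions and gives about 350 mL of blood for PK (Section 11.2).

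**Working it through.** **Inputs.** From Section 16.2: means 3581 and 5586, SD 1920, power 80%. From Sections 16.1 and 16.2: one-sided 2.5%. The within-subject correlation ρ is not given and is varied below.

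Difference Δ = 5586 − 3581 = 2005. Standardised difference d = 2005 / 1920 = 1.044.

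**Step 1: reproduce the protocol's figure.** For a t-test on two independent groups of n, the noncentrality is Δ / (SD × √(2/n)) with 2n − 2 degrees of freedom.

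- n = 15 per group: noncentrality 2.86, power 78.8%.
- n = 16 per group: noncentrality 2.95, power 81.5%.

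So 16 per group is the smallest size that reaches 80%, and 2 × 16 = 32. The dropout step is also right: 32 / 0.9 = 35.6, rounded up to 36.

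Other two-group readings do not give 32 in total:

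- Normal approximation, one-sided 2.5%: 15 per group, 30.
- Two-sided 2.5%: 19 per group, 38.
- One-sided 5%: 13 per group, 26.
- Log scale, with the SD divided by the larger mean, the average mean or the smaller mean as CV: 20, 28 or 44.

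**Step 2: the same inputs in the trial's own design.** For a paired t-test, the SD of the difference is 1920 × √(2(1 − ρ)). The noncentrality is (2005 / SD of difference) × √n with n − 1 degrees of freedom.

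| ρ (assumed) | SD of difference | n for 80% power | Power with 32 completers |
|---|---|---|---|
| −1 (extreme bound) | 3840 | 31 | 81.6% |
| 0 | 2715 | 17 | 98.1% |
| 0.25 | 2352 | 13 | 99.7% |
| 0.5 | 1920 | 10 | above 99.9% |
| 0.7 | 1487 | 7 | above 99.9% |
| 0.8 | 1214 | 6 | above 99.9% |

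The row ρ = 0.5 also covers the reading in which 1920 is itself the SD of the difference.

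**Step 3: can any paired reading give 32?** A paired t-test that has exactly 80% power at n = 32 needs an SD of the difference of about 3922. With a common SD of 1920 the largest possible value is 2 × 1920 = 3840, at ρ = −1, and even there 31 subjects are enough. So none can.

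**Step 4: the planned test.** Simulated power of the one-sided Wilcoxon signed-rank test, with normally distributed differences:

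- ρ = 0: about 78% to 79% at n = 17, 81% to 82% at n = 18, and just under 98% at n = 32.
- ρ = 0.5: about 81% at n = 10, and essentially 100% at n = 32.

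The move from the t-test to the signed-rank test therefore adds about one subject at ρ = 0 and does not close the gap to 32.

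**Step 5: does it matter that the test is paired?** The test's name in Section 16.5.1 mixes the names of the paired and the unpaired Wilcoxon tests. I read it as paired, because it is called signed and each subject receives both products. Even if pairing were ignored, each product would have 32 values, not 16. The noncentrality would be 1.044 × √(32/2) = 4.18, and the two-sample t-test formula would give about 98% power at ρ = 0.

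**The case against.** The strongest reply is that the error is on the safe side. If the correlation is 0 or positive, the trial has far more than 80% power, and the type I error and the primary conclusion are untouched. That stands, and it sets the weight of the point: the statement should be corrected, but the trial does not depend on the correction. A reader who sees a wrong power calculation might infer that the trial is underpowered. The figures show the opposite.

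Second, Section 16.2 names no formula, so the use of a parallel-group calculation is inferred from the match. That also stands. The point does not rest on the inference, because no paired t-test on the stated inputs needs 32 subjects whatever formula was used.

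Third, more subjects may be wanted for the secondary comparisons of flavour, lip placement and the other products. That may be so, but the protocol does not say it: Section 16.2 sizes the trial on the primary hypothesis alone. A reader might go further and fault the protocol for not stating what 32 subjects can detect in those comparisons. The document does not support that criticism. It promises no power for secondary endpoints, and it gives an SD for only two of the seven treatments and only for AUC.

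Fourth, technical detail may sit in a separate statistical analysis plan, as Section 16 announces. That covers what the protocol leaves open. It does not cover a sample size and a power that the protocol itself states.

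**Conclusion.** The point holds. The stated 80% power and requirement of 32 do not belong to a crossover with a paired primary test, and nothing elsewhere in the protocol corrects them. With 32 completers the power is about 98% at within-subject correlation 0 and above 99.9% at 0.5. At correlation 0, 80% power needs 17 subjects (paired t-test) or about 18 (signed-rank test). At 0.5 it needs about 10, and fewer at higher correlation. For the primary comparison alone, 32 is thus nearly twice the required number or more.

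This rests on the protocol's means and SD, on an assumed correlation of 0 or above, and on normally distributed differences for the signed-rank figures. A negative correlation would shrink the gap, but even at the bound of −1 the paired t-test needs 31, not 32.

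The finding does not show that 36 is the wrong number to enrol. It shows that the reason given for 36 is not valid. The 10% dropout allowance is correct.

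**What to change.** In Section 16.2, state the assumed within-subject correlation or the SD of the within-subject difference, from the former studies if they allow it, and restate the power and required number for the paired test. Possible wording, if no estimate is available:

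*With 32 evaluable subjects, the paired one-sided 2.5% test has about 98% power for a difference of 2005 if the SD is 1920 and the within-subject correlation is 0, and more if it is positive. For 80% power, at most about 18 subjects would be needed at correlation 0 or above.*

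If 36 is kept, add a sentence saying that this exceeds what the primary comparison needs, and give the reason. The cost is a rewording of one section. It needs no extra subjects and no change to the design or the primary analysis.

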16.3 Analysis data sets

16.3.1 Full analysis set

The Full Analysis Set (FAS) will consist of all subjects who have been randomised and received at least one dose of IP. This population will be used as the Safety analysis set.

16.3.2 Per protocol set

The Per Protocol Analysis Set (PPS) will consist of all subjects who have been randomised and completed the study without any major protocol deviations that are judged to compromise the analysis of the data. All protocol violations will be judged as major or minor at the clean file meeting. This population will be used as the PK analysis set.

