8.10.3 Subject replacement

Subjects who are prematurely withdrawn from the study may not be replaced during the course of the study.

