10.4 Assessments related to secondary endpoints

10.4.1 Samples for analysis of Methyl salicylate

Plasma samples for determination of plasma concentrations of nicotine will also be analysed for plasma levels of salicylic acid which is a proxy for plasma levels of the flavour component Methyl salicylate. The levels of salicylic acid will be used for read-across to assess the plasma levels of Methyl salicylate.

The analysis of salicylic acid will only be performed for samples drawn during the experimental session when the IP is containing the flavour component i.e. ZYN® Wintergreen 6 mg and Longhorn Wintergreen pouch.

Plasma samples for determination of plasma concentrations of salicylic acid will be analysed by ABS Laboratories Ltd by means of a validated using LC-MS/MS method. Samples from all evaluable subjects excluding withdrawn or dropout subjects will be analysed.

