14.5 Study time table and end of study

The study is expected to start in Quarter 4, 2018 and to be completed by Quarter 1, 2019.

A subject is considered to have completed the study if he/she has completed all visits in the study including visit 9, Follow up.

The end of the study is defined as the date of visit 9, Follow up.

The end of the clinical part of the study is defined as the last visit of the last subject participating in the study.

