16.5 Analysis of primary endpoints

16.5.1 Comparison of total nicotine exposure (AUC_{inf}) after administration of ZYN[®] 6mg and 2 pouches of 8 mg Swedish snus

AUC_{inf} based on plasma concentrations of nicotine after administration of one single dose of ZYN® Smooth 6 mg of nicotine, to that of one single dose 2 pouches of 8mg Swedish snus will be described using summary statistics and non-parametric signed Wilcoxon rank sum test for between treatment difference.

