16.6 Analysis of secondary endpoints

16.6.1 Comparison of PK profiles between all included products

The PK analysis will be based on the PPAS and performed by CTC. The PK parameters will be calculated by non-compartmental analysis (NCA) using the software Phoenix WinNonlin® version 6.3 or later (Pharsight Corporation, U.S.A.).

The following non-compartmental PK parameters will be assessed:

- T_{max} (sampling time at which C_{max} occurred)
- C_{max} (maximum observed concentration)

- AUC_{inf} (area under the curve from 0 to infinity)
- AUC_{last} (area under the curve from 0 to t hours where t is the last measured concentration)

The mean + SD of AUCinf based on plasma concentrations of nicotine after administration of each pouch, will be calculated. AUC_{0-t}, AUC_{inf}, Cmax, Tmax, and terminal half-life will also be calculated.

AUC_{0-t}, AUC_{inf}, Cmax, Tmax, and terminal half-life of all included products will be described using summary statistics and analyzed using signed Wilcoxon rank sum test for between treatment differences for all pairwise comparisons.

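### The PK analysis set requires completion of every visit, including the follow-up telephone call, so a few valid within-subject pairs are discarded without need

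*Protocol*

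**What the plan says.** Section 16.3.2 limits the per protocol set to "all subjects who have been randomised and completed the study without any major protocol deviations" and adds: "This population will be used as the PK analysis set". Section 16.6.1 agrees: "The PK analysis will be based on the PPAS and performed by CTC". The full analysis set in 16.3.1 is wider, but its only stated use is safety.

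Section 14.5 says what completing means: "A subject is considered to have completed the study if he/she has completed all visits in the study including visit 9, Follow up". Table 8.1-1 in section 8.1 labels that visit "Visit 9 Telephone FU" and schedules no blood sampling or pouch use for it.

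The primary comparison in 16.5.1 uses two of the seven sessions, ZYN Smooth 6 mg and two pouches of General PSWL, with a "non-parametric signed Wilcoxon rank sum test for between treatment difference". Section 16.6.1 applies the same test to all pairwise comparisons.

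On assays, 10.3.1 (nicotine) and 10.4.2 (pouches) cover evaluable subjects, a term the protocol does not define. For salicylic acid, 10.4.1 goes further: "Samples from all evaluable subjects excluding withdrawn or dropout subjects will be analysed". Section 8.10.3 states: "Subjects who are prematurely withdrawn from the study may not be replaced".

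**The concern.** In a paired crossover, a comparison of two products needs valid data from the two sessions in which they were used. The rule here asks for all seven sessions and a telephone call. A subject with complete ZYN 6 mg and General profiles who misses one Longhorn session, or cannot be reached by telephone, falls outside the PK set, although neither event affects the two AUCinf values.

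Two things are at stake. The first is precision: each pairwise comparison loses pairs it could have kept, and withdrawn subjects are not replaced. The second is selection. If someone withdraws because of nicotine effects in a session outside the comparison (for the primary comparison, an 18 mg Longhorn session is an example), the pairs already completed go too. Section 6.1 stresses large differences between individuals in uptake, and 6.2 states the aim as ensuring that ZYN does not give higher exposure. A completers-only set could under-represent sensitive users.

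**Working it through.** **Who is excluded.** Section 16.3.2 requires study completion. Section 14.5 equates that with every visit, Visit 9 included. The qualifier in 16.3.2 about compromising the analysis attaches to the deviations, not to completion, so it gives no way back in. The lost-to-follow-up rule in 8.10.1 needs two missed visits plus failed contact, so one missed session can remove a subject from the PK set without making that subject lost to follow-up.

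**The plan's own sample size (16.2).** Inputs: means 3581 and 5586, SD 1920, one-sided 2.5%, power 80%.
- Difference = 5586 − 3581 = 2005; 2005/1920 = 1.044.
- A two-sample t calculation needs 16 per arm, 32 in total (power 81.5%; 15 per arm gives 78.8%). This reproduces the stated 32.
- 32/0.9 = 35.6, rounded up to 36. This reproduces the stated 36, so the planned loss is 36 − 32 = 4 subjects.

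**Pairs discarded.** Assume every order of the seven products is equally likely. A subject who stops after k sessions has then had any given pair of products with probability (k/7) × ((k−1)/6) = k(k−1)/42.

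| k | 1 | 2 | 3 | 4 | 5 | 6 | 7 (only the call missed) |
|---|---|---|---|---|---|---|---|
| Probability | 0 | 0.05 | 0.14 | 0.29 | 0.48 | 0.71 | 1 |

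The protocol gives no distribution of stopping points, so an even spread is an assumption.
- Over k = 1 to 6: mean = (0+2+6+12+20+30)/(42 × 6) = 70/252 = 0.278; 4 × 0.278 = 1.1 pairs.
- Over k = 1 to 7: mean = 112/(42 × 7) = 0.381; 4 × 0.381 = 1.5 pairs.
- Extremes for four dropouts: 0 pairs if all stop after session 1, 4 × 0.714 = 2.9 if all stop after session 6, and 4 if all miss only the call.

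The same figures apply to each of the 7 × 6/2 = 21 pairwise comparisons. Against 32 completers, 1.1 to 1.5 pairs is about 3% to 5%.

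**Effect on primary power.** The least favourable reading considered takes 1920 as the per-treatment SD with zero within-subject correlation. The SD of the difference is then 1920 × √2 = 2715. A paired t test needs 17 pairs for 80% power (18 with a π/3 allowance for the signed-rank test). Paired t power is 98.1% with 32 pairs, about 99% with 36 and about 93% with 24.

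**Unused sessions.** Four dropouts × a mean of 3.5 completed sessions (k = 1 to 6) = 14 sessions.
- Nicotine: 14 × 10 samples (pre-dose plus nine, Table 8.1-1) = 140.
- Salicylic acid: 14 × 2/7 = 4 wintergreen sessions; 4 × 10 = 40 samples.
- Pouches: eight per seven sessions, because General uses two; 14 × 8/7 = 16.

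**The case against.** The strongest reply is that the effect is small and already planned for. The inflation from 32 to 36 allows for four losses, the completer set is the intended 32, and the paired primary test has far more power than it needs. That stands. A reader might infer that the rule leaves the trial underpowered; the protocol's own figures show it does not.

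A reader might also infer that the primary result is biased. The documents do not support that. They give no rate of withdrawal for nicotine effects, and 6.3 regards adverse nicotine effects as unlikely in these habitual users. The contrast is within-subject, so no size or direction of bias follows. Nor does every withdrawal on a high-nicotine product cost a recoverable primary pair: the 16 mg product is General itself, and a subject who stops during that session has no General profile to restore.

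A third tempting inference is that no dropout's samples will be assayed. Only 10.4.1, on salicylic acid, excludes them in terms. If the word evaluable already excluded dropouts, that addition would be redundant, so nicotine samples and pouches of withdrawn subjects may well be assayed. Against this, the synopsis speaks of evaluable subjects completing the study, and 11.3 disposes of PK samples once the study report is final. The ambiguity is worth closing, but it is not a stated exclusion.

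Two further points are fair. The completion definition stands in a section on timelines that 16.3.2 does not cite, and no rate of missed calls is given. Section 16.5.1 also names no analysis set, so the link to the primary endpoint runs through the PK-set statement in 16.3.2 and through 16.6.1. Even so, 14.5 is the protocol's explicit definition of a completer, and AUCinf is a PK parameter. Finally, dropouts' sessions still count in the full analysis set for safety.

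**Conclusion.** The point holds as a defect in the definition of the analysis set with a modest effect. As written, missing any session outside the comparison, or the Visit 9 call, removes a subject's valid ZYN 6 mg and General pair from the PK analysis. The expected loss is about 1.1 to 1.5 primary pairs, and as many in each secondary comparison. This rests on four dropouts, random product order and evenly spread stopping points. Primary power is not materially affected. Section 16.2 sizes only the primary comparison, so no margin is stated for the secondary ones. Selection through withdrawal for nicotine effects is possible but cannot be quantified from the protocol. The change is worth making because the loss is avoidable and the correction is cheap.

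**What to change.** - **16.3.2:** drop the study-completion requirement. Define the PK set as randomised subjects with at least one evaluable PK profile. Exclude individual sessions, not subjects, for major deviations.
- **16.5.1 and 16.6:** base each pairwise comparison on all subjects with evaluable values for both products, and name the set in 16.5.1. Keep the full-completer set as a sensitivity analysis.
- **10.4.1:** remove the exclusion of withdrawn or dropout subjects from the salicylic acid assay.
- **10.3.1 and 10.4.2:** state that evaluable includes the completed sessions of withdrawn subjects, unless consent is withdrawn, in which case 11.5 governs.

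The cost is protocol wording plus, at the planned dropout, up to about 140 nicotine, 40 salicylic acid and 16 pouch assays. The nicotine and pouch assays are extra only to the extent that withdrawn subjects' material would otherwise have been left out. Numbers of subjects will differ slightly between comparisons, so each should be reported with its own count.
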